5.6.3. Clinical Chemistry and Hematology Parameters (Part A only) ([Appendix B](#))

All laboratory data will be summarized by mean, SD, 95% CI, median, Q1, Q3, minimum, and maximum for POD1 Pre-Dose, EOT, and EOS for the active and its matching vehicle placebo groups in Part A in [Table 14.3.5.1](#). The frequencies of shift from Low, Normal, or High, defined by Covance Laboratory Services, to other categories will also be summarized for both treatments in [Table 14.3.5.2](#). All values will be listed for all subjects in the safety population by treatment for POD1 Pre-Dose, EOT and EOS in [Listing 16.2.8.1](#) and [16.2.8.2](#). All values that are out of normal range will be listed in [Table 14.3.4](#) and [Listing 16.2.8.3](#).

5.6.4. Serum Cortisol Concentration (Part A only)

Serum cortisol concentration will be summarized in the same way as other laboratory tests for POD1 pre-randomization and EOT for the active and its matching vehicle placebo groups in Part A in [Table 14.3.5.3](#) and [14.3.5.4](#) and visually presented in [Figures 14.3.5.1](#).

All serum cortisol values and their flags (H or L) defined by Covance Laboratory Services will be listed for all subjects by treatment for Screening and EOT visits in [Listing 16.2.8.4](#). All individual subject values will be visually presented in [Figure 14.3.5.2](#).

5.6.5. Intraocular Pressure

For both eyes at Screening and EOS, the analyses of IOP will follow the methods discussed in Section 5.3.2 for Both eyes at Screening and End of Study (EOS). The results will be presented in the top part of [Table 14.3.6.1](#) and [Table 14.3.6.2](#).

For study eye at POD1-POD22 (Part A) and POD1-POD15 (Part B), the analyses will follow the methods discussed in Section 5.3.2 for “observed data” under Study eye only. The results will be presented in [Table 14.3.6.1](#) and its CFB (Baseline = Screening for EOS; Baseline = POD1/pre-dose for other PODs) for the active and its matching vehicle placebo groups at each visit in [Table 14.3.6.2](#) and visually presented in [Figure 14.3.6.1](#).

The distribution of IOP over the ranges of <10, 10-15, 16-20, 21-25, 25-30, and >30(mmHg) for each treatment will be described by the frequencies in each range in [Table 14.3.6.3](#). The distribution of IOP increase over ranges of ≤ 0 , 1-5, 6-10, 11-15, >15 (mmHg) for the active and its matching vehicle placebo groups will be described by the frequency in each range at each visit in [Table 14.3.6.4](#).

	Document Number: CLN.001.SAP	Version: 0
	Document Title: Clinical Study CPN-201 Statistical Analysis Plan	Page 25 of 35

The number of subjects with an IOP ≥ 24 mmHg AND an increase ≥ 10 mmHg from pre-dose baseline, and the number of subjects with an IOP > 30 mmHg at any time following initiation of study drug will be summarized in the adverse event tables, [Table 14.3.1.1- 14.3.1.3](#).

All subjects' intraocular pressure information will be presented in [Listing 16.2.9.2](#) and visually presented in [Figure 14.3.6.2](#).

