- Pregnancy and Nursing Mothers: [Note: females of child-bearing potential as well as pregnant and/or nursing mothers are excluded from participation in this study.] Corticosteroids have been shown to be teratogenic in laboratory animals when administered systemically at relatively low dosage levels (Pregnancy Category C). When administered subcutaneously, CP was a significant teratogen in both the rabbit and mouse.

Systemically administered corticosteroids appear in human milk and could suppress growth, interfere with endogenous corticosteroid production, or cause other untoward effects. It is not known whether ocular administration of APP13007 could result in sufficient systemic absorption of CP to produce detectable concentrations in human milk.

[REDACTED] plasma CP concentrations in human subjects after ocular instillation of one drop of APP13007 are expected to be lower than that observed in human subjects after dermal application of CP-containing products.

Potential ocular risks are summarized below.

Potential Class-Related Ocular Risks Associated with Corticosteroid Therapies for the Treatment of Ocular Inflammation and Pain after Ocular Surgery

[figure not shown]
The active ingredient in APP13007, [REDACTED] has the following anticipated ocular risks associated with the corticosteroid class:

- Intraocular pressure (IOP) increase – prolonged use may result in glaucoma with damage to the optic nerve, defects in visual acuity and field of vision.
- Cataracts – Prolonged use [REDACTED] may result in posterior subcapsular cataract formation in the non-operated eye.
- Delayed healing – Use [REDACTED] after cataract surgery may delay healing and increase the incidence of bleb formation. In those diseases causing thinning of the cornea or sclera, perforations have been known to occur with the use of topical corticosteroids.
- Risk of Infection
 - Bacterial infections – Prolonged use [REDACTED] may suppress the host immune response and thus increase the hazard of secondary ocular infections. In acute purulent conditions, corticosteroids may mask infection or enhance existing infection.
 - Viral infections – Use of ocular corticosteroids may prolong the course and may exacerbate the severity of many viral infections of the eye (including herpes simplex).
 - Fungal Infections – Fungal infections of the cornea are particularly prone to develop coincidentally with long-term local corticosteroid application. Fungus invasion must

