6.3. Study Visit Schedule for Rescued Subjects

Subjects who meet the criteria for rescue presented in Section 9.4 should discontinue study drug and receive rescue medication. Subjects who are rescued should continue in the study as indicated in Table 5A or Table 5B below. Note that the assessments in the check box under each visit in the Schedule of Events (Table 2A or Table 2B) with a (R) next to “X” indicates that the assessments should be performed on rescued subjects at the indicated visits. Table 5A or Table 5B provides an overview of the study visits and assessments required for rescued subjects depending on when the rescue occurs during the study. It is important to note that (i) subjects rescued on or before POD16 in Part A will be considered as having completed the study before POD28 as indicated by ‘na’ in Table 5A and (ii) subjects rescued on or before POD9 in Part B will be considered as having completed the study before POD22 as indicated by ‘na’ in Table 5B.

Table 5A: Visits for Rescued Subjects (Part A)

Time of Rescue	Protocol Defined Study Visits				
	POD4 (± 1 day)	POD8 (± 1 day)	POD15 (± 1 day)	POD22 (± 1 day)	POD28 (± 1 day)
PODs 2-5	Conduct EOT (POD22) assessments at time of rescue but no later than POD4/5	Complete POD8 assessments in Table 2A marked with an (R)	Complete EOS (POD28) assessments and terminate subject from the study	na	na
PODs 6-9	per protocol	Conduct EOT (POD22) assessments at time of rescue but no later than POD7/8/9	Complete EOS (POD28) assessments and terminate subject from the study	na	na
PODs 10-16	per protocol	per protocol	Conduct EOT (POD22) assessments at time of rescue but no later than POD14/15/16	Complete EOS (POD28) assessments and terminate subject from the study	na
PODs 17-22	per protocol	per protocol	per protocol	Complete EOT (POD22) assessments at time of rescue but no later than POD22/23	Complete EOS (POD28) assessments and termination subject from the study

na = not applicable

Table 5B: Visits for Rescued Subjects (Part B)

Time of Rescue	Protocol Defined Study Visits			
	POD4 (± 1 day)	POD8 (± 1 day)	POD15 (± 1 day)	POD22 (± 1 day)
PODs 2-5	Conduct EOT (POD15) assessments at time of rescue but no later than POD4/5	Complete POD8 assessments in Table 2B marked with an (R)	Complete EOS (POD22) assessments and terminate subject from the study	na

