8. ADVERSE EVENTS

8.1. Definition of Adverse Events (AEs)

Adverse event means any untoward medical occurrence in a subject or clinical investigation subject administered a pharmaceutical product and which does not necessarily have a causal relationship with this treatment (21CFR312.32 (a); ICF E6 Section 1). An AE can therefore be any unfavorable sign and unintended sign (including an abnormal laboratory finding), symptom, or disease temporally associated with the use of a medicinal (investigational) product, whether or not related to the medicinal (investigational) product.

Note:

- *Reporting of AEs that may or may not be related to the ocular surgical procedure depends on their severity:*
 - i. *An AE that the Investigator considers to be within what is normally expected for cataract surgery will be recorded in a table in the source documents and no further reporting is required.*
 - ii. *An AE that the Investigator considers to be outside what is normally expected for cataract surgery or is associated with clinical sequelae will be recorded in the full AE page in the source documents and also in the eCRF,*
- *Rescued subjects are considered to be treatment failures, and rescue itself is not considered an AE.*
- *Adverse events occurring in rescued subjects should be reported in the eCF.*
- *An anterior chamber cell count > 30 on POD1 that leads to disqualification of the subject prior to Randomization should be reported as an AE.*
- *An IOP > 30 mmHg after Randomization should be reported as an AE.*
- *An IOP ≥ 24 mmHg AND an IOP increase ≥ 10 mmHg from pre-dose baseline should be reported as an AE.*

The term “severe” is used to describe the intensity of an AE; the event itself could be of relatively minor clinical significance (e.g., ‘severe’ headache). This is not the same as “serious”. Seriousness of AEs is based on the outcome of an AE and usually associated with events that pose a threat to a subject’s life or functioning.

A Treatment Emergent Adverse Event (TEAE) will be defined as any AE that occurs after the study drug dosing is initiated. For the purpose of this study, a TEAE may be related to the ocular surgical procedure and/or to the initiation of the study drug.

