No formal hypotheses are being tested.

All reported p-values will be considered exploratory and hypothesis-generating.

3. Sample Size Determination

This is a Phase 2a trial to explore dosing regimens, and no formal sample size calculations were used to determine the number of subjects to be enrolled into the trial. The sample size of 21 subjects in each study drug group was selected based on feasibility. Assuming a dropout rate of 5%, approximately 21 subjects will be enrolled into each treatment arm so that approximately 20 subjects per treatment arm would be expected to complete study drug dosing through the POD15 visit.

4. Populations for Analyses

The analysis populations are defined as safety population, intent-to-treat population, and per-protocol population.

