5.1.6.1. Incomplete dates for birthday, adverse events, and medications

The day of birth date will not be collected in order to protect subjects' privacy. To calculate the age from birth date, the day will be assigned as 1st of the birth month.

For analysis of AEs and medications, a complete date should be established in order to determine whether AEs or medications as occurring during study drug or not. For the purpose of handling partially reported start and stop dates for AEs or medications, the following algorithm will be applied:

Missing start day, but month and year present	If study drug had been taken in the same month and year as the occurrence of the AE/medication, then the start day of the event/medication will be assigned to the day of first dose of study drug. Otherwise the start day will be set to the first day of the month.
Missing start day and month, but year present	If study drug had been taken in the same year as the occurrence of the AE/medication, then the start date of the event/medication will be assigned to the date of first dose of study drug. Otherwise the start day and month will be set to 01 January.
Missing end day and month, but year present	The end day and month will be set to the date of end of study. However, if trial termination year is greater than the year of the event/medication, then the day and month will be set to 31December. In subject data listings, start and stop date of AEs or medication will be displayed as reported.

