5.6. Safety Analyses

Safety data will be analyzed for all subjects in the Safety population.

The safety endpoints are:

- Adverse event (AE)
- Serum cortisol concentrations (Part A)
- Clinical chemistry and hematology parameters (Part A) ([Appendix B](#))
- Intraocular pressure (IOP)
- Early Treatment Diabetic Retinopathy Study (ETDRS)

	Document Number: CLN.001.SAP	Version: 0
	Document Title: Clinical Study CPN-201 Statistical Analysis Plan	Page 23 of 35

- Best corrected Visual Acuity by pinhole method
- Slit-lamp biomicroscopy
 - Corneal edema
 - Ciliary flush
 - Bulbar conjunctival injection
- Dilated indirect ophthalmoscopy
 - Vitreous
 - Retina
 - Macula
 - Choroid
 - Optic nerve

See Section 7.2 of the protocol for detail about these endpoints. The analyses of these safety endpoints are described in the following sub-sections.

For all safety endpoints, the total number of subjects in the safety population and the summary statistics of all observed data will be calculated for each active dosing regimen and its matching vehicle placebo group and each visit as defined in the CRF. No imputation will be used.

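### Adverse-event and IOP-threshold counts have no cut-off at rescue and no time at risk, so events after a switch to rescue medication are counted with the study-drug arm

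*SAP*

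**What the plan says.** **Safety data rule.** For all safety endpoints, SAP 5.6 states that "the total number of subjects in the safety population and the summary statistics of all observed data will be calculated", by CRF-defined visit and without imputation.

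**AE counts.** Protocol 8.1 says a treatment-emergent event "will be defined as any AE that occurs after the study drug dosing is initiated"; no end of the window is given. SAP 5.6.2 breaks AEs down by location, seriousness, relationship and severity, but not by whether the subject was still on study drug. SAP 5.1.6.1 completes partial dates "in order to determine whether AEs or medications as occurring during study drug or not", yet no table is described as using that status. Exposure (SAP 5.6.1) is a count of drops instilled, not days.

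**IOP counts.** SAP 5.6.5 puts two threshold counts into the AE tables. For one, the "number of subjects with an IOP > 30 mmHg at any time following initiation of study drug will be summarized". The other needs at least 24 mmHg together with a rise of at least 10 mmHg from pre-dose baseline.

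**By-visit IOP.** For the study eye at POD1 to POD22 (Part A) or POD15 (Part B), SAP 5.6.5 refers to the observed-data method of SAP 5.3.2. That method uses only data from subjects still on study drug, which SAP 5.1.6.2 defines as first dose to two days after last dose. EOS IOP is tabulated against Screening.

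**Rescue.** Under Protocol 5.4.1 and 9.4.1 a rescued subject stops study drug and receives a drug of the investigator's choice. Protocol 6.3 (Table 5A) then shortens Part A follow-up for most rescue times: "Complete EOS (POD28) assessments and terminate subject from the study" at POD15 for rescue by POD9, and at POD22 for rescue on PODs 10-16. Table 5B ends Part B follow-up at POD15 for rescue by POD9. Later rescues keep the full schedule.

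**The concern.** The primary safety objective compares APP13007 with its vehicle. Protocol 1.4.1 says the active ingredient "has the following anticipated ocular risks associated with the corticosteroid class", and IOP increase heads the list. Protocol 1.2.2 gives corticosteroids as its example of what is usually prescribed after cataract surgery. If a vehicle subject is rescued onto such a drug and IOP then passes a threshold, the event is counted on the vehicle side and the contrast shrinks. If the rescued subject instead leaves early, late events go unobserved and the vehicle count falls. The planned AE and threshold tables cannot show which effect is present.

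The SAP expects the arms to differ in time on drug: SAP 5.3.2 notes that the number still on study drug will itself reflect a treatment difference. For efficacy it uses the on-study-drug definition to keep post-rescue values out. For AEs and the threshold counts it does not use it.

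**Working it through.** **1. The plan's own figure.** SAP Section 3: "Assuming a dropout rate of 5%, approximately 21 subjects will be enrolled into each treatment arm". 20/0.95 = 21.05 and 21 x 0.95 = 19.95, so 21 per arm is reproduced; 6 x 21 = 126. The plan states no figure for post-rescue events or time at risk. One subject is 1/21 = 4.8 percentage points.

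**2. Follow-up by time of rescue** (nominal days from POD1, Tables 5A and 5B; a completer has 28 - 1 = 27 days in Part A and 22 - 1 = 21 in Part B).

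| Part | Rescue | EOS | Days followed | Days lost | Days after rescue |
|---|---|---|---|---|---|
| A | POD4 | POD15 | 14 of 27 | 13 | 11 (79%) |
| A | POD8 | POD15 | 14 of 27 | 13 | 7 (50%) |
| A | POD15 | POD22 | 21 of 27 | 6 | 7 (33%) |
| A | POD22 | POD28 | 27 of 27 | 0 | 6 (22%) |
| B | POD4 | POD15 | 14 of 21 | 7 | 11 (79%) |
| B | POD8 | POD15 | 14 of 21 | 7 | 7 (50%) |
| B | POD15 | POD22 | 21 of 21 | 0 | 7 (33%) |

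The safety objective runs to POD22 in Part A (21 days) and POD15 in Part B (14 days). Inside that window, Part B rescue by POD9 loses nothing (14 of 14), nor does Part A rescue on PODs 10-16 (21 of 21). Only Part A rescue by POD9 loses time: 14 of 21 days.

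**3. Vehicle subject-days** (assumed: 10-50% rescued, at POD4 or POD8). Example, Part A, 30% at POD4: 6.3 subjects rescued; 14.7 x 27 + 6.3 x 14 = 485 of 21 x 27 = 567 days (86%); 6.3 x 11 = 69 days after rescue (14% of 485). Across the range, 76-97% of full subject-days are observed and 3-31% of those fall after rescue.

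**4. Effect on an any-time IOP count** (illustration). Assumptions, none from the documents: constant daily hazard; event risk per treatment course 10% or 20% on a steroid and 2% off; rescue 10/30/50% on vehicle with 0/5/10% on active; rescue drug a steroid.

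- Hazard h = -ln(1 - p)/course length, with 21 dosing days in Part A and 14 in Part B.
- No rescue: active risk = 1 - exp[-(h_on x dosing days + h_off x remaining days)]; vehicle risk = 1 - exp(-h_off x full follow-up).
- Rescued on day r, vehicle: 1 - exp[-(h_off x (r - 1) + h_on x (15 - r))]. Rescued active subjects stay at h_on to POD15.

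Mildest case (Part A, 10% risk on steroid, 10% vehicle rescue at POD8): the difference falls from 0.080 to 0.078, 98% retained. Most extreme (Part B, 20% risk, 50% vehicle rescue at POD4): 0.178 to 0.110, 62% retained.

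| Vehicle rescue | Difference retained |
|---|---|
| 10% | 92-98% |
| 30% | 77-92% |
| 50% | 62-86% |

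The shrinkage is therefore 2-38%, or 0.03 (0.57 - 0.54) to 1.4 (2.04 - 0.63) extra expected vehicle events per 21 subjects.

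**5. Direction if the rescue drug is not a steroid.** Part A: h_off = -ln(0.98)/21 = 0.000962. A rescued vehicle subject's risk is 1 - exp(-0.000962 x 14) = 1.34%, against 2.56% over 27 days. With 10% vehicle rescue and none on active, vehicle risk is 0.9 x 2.56 + 0.1 x 1.34 = 2.44%. With active risk at 10.52% the difference becomes 8.08 rather than 7.95 points, slightly larger instead of smaller.

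**6. The two IOP rules.** SAP 5.6 (repeated in 5.1.6.2) uses all observed safety data, and 5.6 adds CRF visits; 5.1.5.2 limits windowed visits to efficacy. SAP 5.6.5 sends by-visit IOP to the 5.3.2 method, which is on-drug and uses windowed visits. Both cannot apply to Tables 14.3.6.1 and 14.3.6.2. The choice matters because the SAP Appendix adds between-arm comparisons of IOP means and changes.

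**The case against.** The strongest reply is that the main IOP comparison is already protected: by-visit study-eye IOP and its change from baseline point to on-drug data. That stands. A reader might infer that no safety output separates on-drug from post-rescue data; SAP 5.6.5 contradicts this for by-visit IOP. What remains is the AE counts, the two threshold counts and the EOS summary, together with the conflict between 5.6 and 5.6.5.

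A reader might also infer that rescued subjects always leave early. Part A rescue on PODs 17-22 and Part B rescue on PODs 10-16 keep full follow-up, and most of the lost time lies outside the safety objective's window. Subjects given alternative medication without meeting the rescue criteria are withdrawn with EOS assessments at that point, so they contribute no later scheduled visits.

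There are real mitigations. AEs are split by relationship, Table 14.2.1 shows on-drug and rescued numbers by visit, and rescue, AEs, medications and individual IOP are all listed, so at about 21 per arm single events can be traced. These help only in part: relatedness is a masked judgement, and rescue counts by visit do not date events. EOS was never an on-drug comparison, since completers are also off study drug by then, but it still pools them with rescued subjects who may be on another drug at POD15 or POD22.

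Finally, this is a descriptive Phase 2a study (SAP Section 2: "No formal hypotheses are being tested"), for which all-observed counts are a legitimate summary. That is why the fix adds to them rather than replacing them. The table layouts are not visible in the copy reviewed, so the point rests on the SAP's text.

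**Conclusion.** The point holds in limited form. AE counts and both IOP threshold counts have no described cut-off at rescue and no time at risk, and EOS IOP mixes subjects in different treatment states on different days. This can distort the APP13007-versus-vehicle comparison if rescue differs by arm.

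It would go too far to say that it does distort the comparison, or that a null AE or IOP difference would be uninterpretable. The documents give no rescue rate by arm and do not fix the rescue drug class. Under the assumed 10-50% vehicle rescue onto a steroid, the IOP-event difference shrinks by about 2-38%; at 10% rescue the loss is at most 8%. With a non-steroid rescue drug the effect can reverse slightly, so the net direction is open. Nor does the SAP say that safety is tabulated by randomized arm: SAP 1.1.2 speaks of display labels with actual treatment dose. It is a worthwhile, inexpensive improvement to a descriptive analysis. The conflict between SAP 5.6 and 5.6.5 needs resolving in any case.

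**What to change.** - **SAP 5.6.2 and 5.6.5:** keep the all-observed tables. Beside them, give the AE counts and both IOP threshold counts for (a) on study drug, using the SAP 5.1.6.2 definition but ending at the first rescue or alternative medication if that is earlier, and (b) after that point. State subject-days at risk per arm and period.
- **EOS IOP:** show rescued subjects separately.
- **SAP 5.6 and 5.6.5:** reconcile the data rule and visit definition for by-visit IOP, and say which rule the IOP range tables follow.
- **Reporting:** present the on-drug table alongside the all-observed one, not in place of it. Cutting at rescue conditions on an event after randomization, so neither table alone should carry the safety statement.

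Cost: SAP wording and extra columns. Dosing diaries, concomitant-medication start dates, rescue status and AE records are already in the eCRF. The drawback is that small counts are spread over more cells.

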5.6.6. Visual Acuity Worsening from Baseline

The number of subjects with a visual acuity worsening of ≥ 2 lines (equivalent to ≥ 0.2 logMAR CFB), together with ≤ 0 (≤ 0 logMAR CFB) and in between ($0 < \text{logMAR CFB} < 0.2$) at EOS from Screening and at each visit during POD4-POD22 (Part A) and POD4-POD15 (Part B) from POD1/pre-dose visit will be summarized in [Table 14.3.6.5](#).

As mentioned earlier, all subjects' best correct visual acuity information will be presented in [Listing 16.2.6.3](#).

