6.2.7. Subject Early Termination

Subjects who are terminated from the study early, but the rescue criteria in Section 9.4.1 are not met, should have POD28/EOS (Part A) or POD22/EOS (Part B) assessments performed at the time of termination, or as soon thereafter as possible. At early termination the ocular assessments are to be performed on both eyes.

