9. SAFETY MANAGEMENT

9.1. Stopping Criteria

- Individual subject: Subjects with an IOP at POD1/pre-randomization > 30 mmHg will not be eligible for randomization and thus not enrolled in the study. After randomization to study drug, subjects with an IOP > 30 mmHg may continue the study drug and be treated with IOP lowering medication at the discretion of the Investigator. (Note: use of a prostaglandin-based treatment to lower IOP is prohibited).
- Individual subject: Subjects with an IOP > 30 mmHg after randomization who do not respond to IOP lowering therapy should discontinue study drug and should be treated at the Investigator's discretion. These subjects will continue in the study with scheduled assessments to be performed at each visit until EOS/POD28 (Part A) or EOS/POD22 (Part B).
- Individual subject: In consultation with the Study Medical Monitor, the Investigator should consider whether to stop study drug and rescue a subject with an IOP ≥ 24 mmHg AND an IOP increase ≥ 10 mmHg from pre-dose baseline (both criteria must be met).
- Study Treatments: Part A of the study will be conducted as planned. Key data (ACC, pain score, IOP, number of subjects rescued and AEs) from Part A will be evaluated by the Data Review Group in a masked manner and if necessary by the Sponsor Medical Monitor and Sponsor statistician in an unmasked manner after freezing the key data to determine whether Part B is to be conducted as planned. See Section 3.3 and Section 3.4 for further information on the decision-making process to determine whether Part B is conducted as planned or which alternative treatment option is to be used. The study sites, IRB and FDA will be informed of any changes to the planned treatment arms in Part B of the protocol before the changes are implemented.
- Study: The study can be stopped at any time if deemed necessary by the Sponsor's Medical Monitor in consultation with the Study Medical Monitor due to safety concerns. Additionally, safety will be monitored on an ongoing basis by the Data Review Group via periodic masked review of AEs and other safety endpoints. Specifically, if it is observed that visual acuity worsens by 2 lines at EOS in the treated study eye as compared to POD1, in 6 consecutive subjects, no further doses of study drug will be administered to any subjects in the study until

a comprehensive evaluation can be performed and, if possible, a cause is identified.

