10.3.3. Analysis of Safety

Analysis of safety data will be performed for all subjects in the Safety Population.

Adverse events (AE) will be summarized by total number of any AE, number of subjects reporting the AE, ocular AEs (affecting the study eye and/or the non-study eye and/or both eyes, when appropriate), ocular TEAEs in the study eye, systemic AEs, SAEs, suspected unexpected serious adverse reaction (SUSARs), discontinuing study drug due to an AE, by relationship to study drug and/or ocular surgical procedure, and by severity. Adverse events will be coded using Medical Dictionary for Regulatory Activities (MedDRA, most current version) and categorized by system organ class and preferred terms.

The analyses of IOP will include the summary statistics of IOP and its change from baseline (POD1/pre-dose) at each visit, the proportion of subjects with an IOP ≥ 24 mmHg AND an increase ≥ 10 mm Hg from pre-dose baseline, and the proportion of subjects with an IOP > 30 mmHg at any time following initiation of study drug.

The proportion of subjects with a visual acuity worsening from POD1/pre-dose visit of ≥ 2 lines will also be summarized.

Ocular symptoms, comfort grading assessment, ophthalmoscopy findings, and slit lamp biomicroscopy results will be categorically summarized.

Details of statistical analyses will be included in the SAP.

10.3.4. Interim Analysis:

No interim analyses are planned for this study.

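### The SAP's by-visit IOP rule contradicts its own all-observed-data rule for safety, and EOS change in IOP and acuity is set only against Screening, not POD1

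*SAP*

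**What the plan says.** **IOP, data used.** SAP 5.6.5 states: "For study eye at POD1-POD22 (Part A) and POD1-POD15 (Part B), the analyses will follow the methods discussed in Section 5.3.2", and points to the observed-data part of that section. That part of SAP 5.3.2 keeps readings only while the subject is on study drug and assigns them to PODs by the Table F windows. SAP 5.1.6.2 ends the on-drug period two days after the last dose.

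Three other SAP rules say something different. Section 5.1.5.2 reserves the windowed visit variable for efficacy. Section 5.1.6.2 has safety endpoints summarized from all observed data. Section 5.6 repeats this, by CRF visit and without imputation. The SAP Appendix (Modifications) adds between-arm comparisons of IOP means and changes and gives no data rule of its own.

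On subjects who stop study drug because IOP above 30 mmHg does not respond to treatment, Protocol 9.1 says: "These subjects will continue in the study with scheduled assessments to be performed at each visit".

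**IOP, baseline.** Protocol 10.3.3: "The analyses of IOP will include the summary statistics of IOP and its change from baseline (POD1/pre-dose) at each visit". SAP 5.6.5 uses Screening as the baseline at EOS and POD1 elsewhere. SAP 6.6, which lists changes to protocol-planned analyses, names only the ACC-grade addition.

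**Vision.** Protocol 10.3.3: "The proportion of subjects with a visual acuity worsening from POD1/pre-dose visit of ≥ 2 lines will also be summarized". Protocol 9.1 describes its study-level signal with the words "if it is observed that visual acuity worsens by 2 lines at EOS in the treated study eye as compared to POD1". SAP 5.6.6 counts losses of two lines or more "at EOS from Screening and at each visit during POD4-POD22 (Part A) and POD4-POD15 (Part B) from POD1/pre-dose visit will be summarized".

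**Early EOS exams.** For rescue on PODs 2-5 or 6-9 in Part B, the POD15 column of Table 5B reads "Complete EOS (POD22) assessments and terminate subject from the study". Under Protocol 6.2.7, subjects terminated early without meeting rescue criteria "should have POD28/EOS (Part A) or POD22/EOS (Part B) assessments performed at the time of termination".

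**The concern.** Safety is the first-listed objective and this is the first human use of the product. IOP rise is a named class risk.

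Two programmers could each follow the SAP and produce different by-visit IOP tables. The literal version of SAP 5.6.5 loses the off-drug readings of subjects who stop dosing but stay in follow-up, including those who stopped because of IOP. Those readings would leave the by-visit means, the changes from baseline and the added between-arm comparison.

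The EOS baseline raises a separate issue. Screening precedes cataract removal, so change from Screening mixes the effect of surgery with whatever happened after dosing began. For IOP, the protocol asked for POD1 at each visit. For vision, the protocol's own signal is EOS against POD1, and no planned table expressly makes that count.

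**Working it through.** **1. The plan's own threshold.** Protocol 7.3.2 scores 0.02 logMAR per letter. With 5 letters per line (an assumption; the documents do not state it), 2 × 5 × 0.02 = 0.20 logMAR. This matches SAP 5.6.6.

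**2. IOP readings lost under the literal rule.** A reading is dropped if visit day − last-dose day > 2. Nominal post-dose days are 4, 8, 15 and 22 (Part A) and 4, 8 and 15 (Part B). The last dose is taken on the day shown, and all later visits are assumed to be kept.

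| Last dose | Part A dropped | Part B dropped |
|---|---|---|
| POD4 | 8, 15, 22: 3 of 4 | 8, 15: 2 of 3 |
| POD8 | 15, 22: 2 of 4 | 15: 1 of 3 |
| POD15 | 22: 1 of 4 | not applicable |
| Completed (POD21 / POD14) | 0 of 4 | 0 of 3 |

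For completers seen on schedule the EOT gap is 22 − 21 = 1 or 23 − 21 = 2 days in Part A, and 15 − 14 = 1 or 16 − 14 = 2 in Part B, so the reading is kept. Varying days within the visit windows changes one case only: last dose on day 5 with the POD8 exam on day 7 (gap 2, kept). A late EOT exam on days 24-25 (Part A) or 17-18 (Part B) lies inside its Table F window, but its gap is 3-4 days and it is dropped.

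**3. Who can lose readings.** The table fits only subjects who stop drug and keep the full visit schedule. For the others, taking the rescue exam as done at rescue (Protocol 9.4.1):

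| Subject | Exams after stopping (Protocol 6.2.7, Tables 5A/5B) | POD readings dropped |
|---|---|---|
| Rescued PODs 2-5 | EOT exam at rescue, POD8, then EOS exam in the POD15 slot | at most POD8 |
| Rescued PODs 6-9 | EOT exam at rescue, then EOS exam in the POD15 slot | 0 |
| Rescued PODs 10-16 | EOT exam at rescue, then EOS exam in the POD22 slot | 0 |
| Rescued PODs 17-22 (Part A) | EOT exam at rescue, then EOS exam at POD28 | 0 |
| Withdrawn | EOS exam at termination | 0 |

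EOS readings are tabulated separately and are not dropped.

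**4. Averaging within a window.** If Table F applies, SAP 5.1.9 averages visits that share a window. With assumed readings of 34 mmHg on POD8 and 18 on POD10, the POD8 value becomes (34 + 18)/2 = 26. With 21 subjects per arm, the arm mean moves by (34 − 26)/21 = 0.38 mmHg for one such subject and 3 × 8/21 = 1.14 for three.

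**5. Vision at EOS.** Let g be the lines gained from Screening to POD1. The documents do not give its sign or size, so a range is shown. At 0.1 logMAR per line, a true 2-line loss from POD1 appears against Screening as 0.2 − 0.1g. The loss after POD1 needed to be flagged is 2 + g lines.

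| g | Change vs Screening for a 2-line loss from POD1 | Loss after POD1 needed to be flagged |
|---|---|---|
| −2 | +0.4 (flagged) | 0 lines |
| −1 | +0.3 (flagged) | 1 |
| 0 | +0.2 (flagged) | 2 |
| 1 | +0.1 (middle class) | 3 |
| 2 | 0.0 (no worsening) | 4 |
| 4 | −0.2 (no worsening) | 6 |

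The count is undistorted only at g = 0. A positive g hides losses. A negative g flags subjects who lost less than two lines after POD1, or none.

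**The case against.** **On IOP.** The reference to observed data may have meant only that LOCF is not used, since that is the contrast SAP 5.3.2 draws. The on-drug sentence there also covers a list of endpoints that does not include IOP, and three explicit safety rules point the other way. That is a plausible intent, but the method referred to carries the on-drug and Table F conditions, so the text still conflicts and needs a sentence to settle it.

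A reader might infer that every early-stopping or rescued subject loses most of the IOP readings. Tables 5A/5B and Protocol 6.2.7 do not support this, because most such subjects have no later POD visits to lose. A reader might also infer that IOP spikes vanish from the report. They do not: counts of subjects crossing the IOP thresholds are planned in the AE tables (for above 30 mmHg, explicitly at any time after dosing starts), and Listing 16.2.9.2 and Figure 14.3.6.2 show individual values.

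**On vision.** Protocol 9.1 is a halt trigger described with ongoing masked review; it does not prescribe a final table. Protocol 10.3.3 names no visits for vision, SAP 5.1.7 openly prespecifies Screening for EOS, and POD1-based counts run through EOT, which covers the period of the primary safety objective. Listing 16.2.6.3 holds the acuity values. All of this stands. The stronger inference, that the SAP breaches the protocol or leaves the vision signal unmonitored, is therefore not supported.

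**On a simple remedy.** Ordering IOP by CRF visit alone would create a new fault. A rescue-day EOT exam, possible as early as PODs 2-5, could land in the POD22 or POD15 row, and unscheduled readings would have no stated place.

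**Conclusion.** Three conclusions of different weight follow.

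- **By-visit IOP data rule: wrong as written.** The SAP contradicts itself. Under the literal reading the loss falls on subjects who stop drug but keep full visits, such as the IOP non-responders in Protocol 9.1. It runs from 1 to 3 of 4 readings in Part A and 1 to 2 of 3 in Part B, assuming nominal visit days and last dose on a visit day. The documents do not give the number of such subjects. The effect is on means, changes and the Appendix comparison, not on detection of spikes, and p-values are descriptive.
- **IOP change at EOS: a departure from Protocol 10.3.3.** It is stated in SAP 5.6.5 but missing from the list of changes in SAP 6.6.
- **Vision at EOS: a cheap improvement.** The Screening comparison answers a different question from the protocol's EOS-versus-POD1 signal and can hide or over-flag a loss after POD1, depending on the unknown g. POD1 acuity may itself reflect early post-surgical inflammation, so neither comparator suffices alone.

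**What to change.** **SAP 5.6.5, data rule.** State that by-visit IOP uses all observed readings, on or off drug, at the scheduled visit. An EOT exam done early at rescue is shown at the POD at which it took place, not in the POD22 or POD15 row. Unscheduled readings neither replace scheduled ones nor are averaged into them, but they count in the any-time threshold counts and appear in listings. The same rule governs the comparison added in the SAP Appendix. An on-drug display may be kept as secondary.

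**IOP change at EOS.** Add study-eye change from POD1 alongside change from Screening.

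**Table 14.3.6.5.** Add a study-eye EOS-versus-POD1 block, including EOS exams done early in rescued and withdrawn subjects, and keep EOS versus Screening beside it.

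**Cost.** A few sentences in an SAP addendum or in the study report's account of deviations, one IOP change row and one vision block, all from data already collected. The downside is slightly more table work. The POD1 vision results need a note that POD1 acuity may be affected by recent surgery.
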